## **1.0 Rationale and Specific Aims:**

The development of type 2 diabetes mellitus is a significant complication for long-term cancer survivors including patients treated with allogeneic hematopoietic stem cell transplantation (HCT). New onset, post-transplant diabetes mellitus (PTDM) occurs in up to 60% of HCT recipients and negatively impacts transplant survival (1). Currently 8,000 HCT's are performed each year in the United States primarily for patients with high risk hematological disorders. These individuals comprise a well defined group that is at significant risk for developing new metabolic abnormalities including PTDM.

We have found that PTDM resembles type 2 diabetes mellitus. Normally, type 2 diabetes mellitus results from a combination of insulin resistance and decreased insulin secretion. The transition from compensated insulin resistance to frank diabetes occurs as a result of  $\beta$ -cell failure mediated by metabolic overload and inflammation. In animal models, loss of IL-33 signaling through its receptor serum STimulation-2 (ST2) decreases immunosuppressive ST2+ regulatory T cells (Tregs) in visceral adipose tissue, increases Th1 inflammation, worsens insulin resistance, and promotes  $\beta$ -cell stress and diabetes conversion. We found that new-onset PTDM is characterized by: 1) elevated fasting C-peptide levels pre-HCT; 2) impaired islet response to hyperglycemia and GLP-1 after HCT with decreased  $\beta$ -cell insulin secretion and blunted  $\alpha$ -cell suppression; and 3) increased post-transplant serum levels of soluble ST2 (sST2), a decoy receptor which sequesters IL-33. We hypothesize that in PTDM, initial  $\beta$ -cell compensation progresses to exhaustion during the course of HCT, which coincides with increased tissue demand for insulin due to changes in IL-33 signaling, inflammation, and/or hyperglucagonemia. We propose to test this hypothesis with the following aims in a prospective, observational study in HCT recipients.

**Specific Aim 1. To determine if changes in islet cell physiology are detectable before or after matched related donor (MRD) HCT in patients developing new-onset PTDM.**

**Subaim 1A. To determine if a compensatory increase in glucose stimulated insulin secretion (GSIS) by  $\beta$ -cells precedes PTDM development in patients without diabetes undergoing MRD HCT.** Based on our C-peptide and oral glucose tolerance test (OGTT) data, we hypothesize that PTDM-prone individuals maintain euglycemia pre-transplant via enhanced  $\beta$ -cell secretory capacity followed by progressive  $\beta$ -cell dysfunction and relative insulin insufficiency after transplant. In a prospective MRD HCT cohort without diabetes,  $\beta$ -cell function and secretory capacity will be directly measured with hyperglycemic clamps before and 90 days after transplant.

**Subaim 1B. To determine if excess glucagon secretion and impaired  $\alpha$ -cell response to glucose or GLP-1 contributes to the hyperglycemia of PTDM.** We will test the hypothesis that PTDM patients have increased glucagon levels and that glucose and GLP-1 induced  $\alpha$ -cell suppression are incomplete. To assess  $\alpha$ -cell dysregulation, glucose-induced glucagon suppression will be measured during a hyperglycemic clamp and during 2 OGTTs either with or without GLP-1 infusion, before and 90 days after HCT.

**Specific Aim 2. To determine if the IL-33/ST2 axis promotes immune/islet cell dysregulation during PTDM.** We hypothesize that PTDM is characterized by decreased protective IL-33/ST2 signaling in adipose tissue at rest (*i.e.* pre-transplant)

followed by increased systemic, inflammatory signaling during stress (*i.e.* post-transplant), which leads to  $\beta$ -cell compensation and exhaustion, respectively. To investigate the ST2 pathway, we will measure adipose and plasma levels of IL-33 and sST2 and quantify ST2 expression on circulating Tregs and Th1 cells before and after HCT from our MRD cohort. IL-33 effects on T cells and on human islet function will be assessed *in vitro*.

## 2.0 Introduction and Background

### *Role of HCT*

Over 30,000 allogeneic HCTs are performed yearly, with the primary indication being hematological malignancy (2). Although malignancy relapse is the most important cause for death after transplant, HCT recipients who are cured of cancer continue to be at increased risk of developing significant secondary medical conditions that can impact transplant survival negatively (3, 4). Of particular interest is PTDM, due to its high prevalence after transplant and its detrimental effects on cardiovascular health (5, 6).

### *Impaired glucose homeostasis in HCT recipients (PTDM)*

HCT recipients are over 3 times more likely to report a diagnosis of diabetes than their sibling counterparts (7). Our prospective data indicates that early onset PTDM occurs in up to 60% of individuals with no history of diabetes, and it can persist long-term in about 10-30% of these patients with a negative impact on survival (1, 6-11). Risk factors for diabetes in HCT recipients have been described including: older age, nonwhite ethnicity, steroid exposure, and total body irradiation, however the actual mechanisms causing PTDM are unknown (1, 6, 7, 10-13). We have found that new-onset PTDM is characterized by: 1) elevated fasting C-peptide levels pre-HCT; 2) impaired islet response to hyperglycemia and GLP-1 after HCT; and 3) increased post-transplant serum levels of soluble serum STimulation-2 (sST2), a decoy receptor which sequesters IL-33 (1, 14). We hypothesize that in PTDM, initial  $\beta$ -cell compensation progresses to exhaustion during the course of HCT, which coincides with increased tissue demand for insulin due to changes in IL-33 signaling, inflammation, and/or hyperglucagonemia.

Type 2 diabetes mellitus results from a combination of impaired tissue response to insulin action and decreased insulin secretion. Due to compensatory changes in  $\beta$ -cell function, frank hyperglycemia occurs when pancreatic  $\beta$ -cells can no longer meet the insulin demands needed for glycemic control, an event termed  $\beta$ -cell failure. Distinct to transplantation is the use of diabetogenic immunosuppressive medications. There are at least 3 lines of evidence indicating that PTDM is not just an iatrogenic complication of immunosuppressive drugs. 1) Despite near universal treatment of HCT recipients with calcineurin inhibitors, not all patients develop PTDM. 2) The diagnosis of PTDM generally precedes corticosteroid treatment (1, 8, 14). 3) Rates of diabetes among HCT survivors off of immunosuppression are still higher compared to their sibling controls. Therefore the assumption that PTDM is merely a manifestation of diabetogenic medications is flawed (7). Since islet cells are major regulators of glucose homeostasis, their physiology during PTDM needs to be investigated with validated techniques including the oral glucose tolerance test (OGTT) and hyperglycemic clamp.

### *IL-33/ST2 axis and immune/metabolic dysregulation*

Type 2 diabetes mellitus is an inflammatory disease characterized by the accumulation of IFN- $\gamma$  secreting T cells (Th1 cells) and depletion of immunosuppressive Foxp3 $^{+}$  regulatory T cells (Tregs) in adipose tissue (15-18). The balance between Th1 cells and Tregs is a critical determinant of insulin sensitivity/demand which in turn influences  $\beta$ -cell function and stress. IL-33 is a dual cytokine with both inflammatory and regulatory functions. Normally, adipose tissue expresses IL-33, however cytokine levels are lower during obesity and insulin resistance (19). The IL-33 receptor, serum STimulation-2 (ST2) can exist as a membrane bound protein on immune cells including Tregs but not usually Th1 cells, or as a soluble form (sST2) where it functions as a decoy receptor sequestering excess IL-33 (19, 20). In pre-clinical obesity models, the administration of IL-33 increases ST2+Tregs in adipose tissue and improves glucose tolerance compared to PBS-injected control animals (21, 22). Resolution of visceral adipose tissue inflammation by ST2+Tregs decreases insulin requirements and improves fasting blood glucose levels (17, 18). Similarly, our collaborators have shown in a murine model of GVHD, that blockade of sST2 with a neutralizing antibody increased IL-33, expanded ST2+Tregs, decreased inflammation, and improved transplant survival (20). However IL-33 functions as a double-edged sword. In the setting of HCT where multiple noxious stimuli are present, Th1 cells which usually do not express ST2, can acquire the receptor and become responsive to IL-33 released from damaged tissue resulting in lethal alloreactivity (23-25). Theoretically, this ST2+Th1 response could exacerbate inflammation leading to impaired insulin action, increased insulin demand, and increased  $\beta$ -cell work after HCT. IL-33 also directly induces  $\beta$ -cell endoplasmic reticulum stress which accompanies the insulin secretory defect of type 2 diabetes (26). Thus, the IL-33/ST2 axis could affect PTDM conversion through several different mechanisms depending on the differential expression of ST2 by Tregs or Th1 cells, or whether IL-33 exerts its action predominantly in the periphery by determining insulin needs or by affecting  $\beta$ -cell function directly. Although IL-33's influence on glucose homeostasis during periods of quiescence have been described, IL-33's metabolic affects following transplant of an allogeneic immune system and in the presence of ST2+Th1 cells during HCT is unknown.

### *Rationale and clinical application*

HCT recipients are at significant risk for developing new-onset PTDM, which in turn confers inferior survival. The initiating events and mechanisms that culminate in PTDM development remain understudied, and formal recommendations for screening and treatment are lacking. In this proposal, we will use OGTT and hyperglycemic clamps to characterize the onset and role of pancreatic  $\beta$ - and  $\alpha$ -cell dysfunction in metabolic complications after HCT. These results will be adapted into future screening tools for PTDM and translated into therapeutic clinical trials targeting either insulin insufficiency or glucagon excess. By analyzing IL-33 signaling and ST2 expression on Tregs and Th1 cells sequentially before and after transplant, we will 1) investigate the relationship between islet function and ST2 immune regulation during HCT, 2) establish an immune timeline for the development of PTDM, and 3) develop a biological rationale for why treatment/ prevention of metabolic complications could alter ST2 signaling and improve HCT outcomes. We propose that understanding the immunology and the metabolic abnormalities generating PTDM will promote rapid improvements in the care of HCT recipients.

### 3.0 Preliminary Data

[figure not shown]
#### *Incidence and risk factors for early PTDM*

We prospectively analyzed PTDM incidence (defined as a weekly fasting glucose  $\geq 126$  mg/dL or random glucose  $\geq 200$  mg/dL) during the first 100 days of HCT in 84 patients without diabetes (1). New-onset PTDM was diagnosed in 50 (60%) patients at a median of 23 days after HCT and prior to the start of steroids in the majority. PTDM was associated with inferior survival when analyzed in a time-dependent manner [hazard ratio (HR), 3.27; 95% confidence interval (CI), 1.3-8.2;  $P=0.01$ ]. In multivariate analysis, elevated, pre-transplant fasting C-peptide level independently predicted both new-onset PTDM [odds ratio (OR), 5.9; 95% CI, 1.77-20.22;  $P=0.004$ ] and increased mortality (HR, 1.05; 95%CI, 1.01-1.09;  $P=0.013$ ) (1). This prospective study indicates that compensatory  $\beta$ -cell changes, as evidenced by increased fasting C-peptide level, could be present prior to HCT (and before exposure to immunosuppression) and that changes in glucose metabolism could lead to inferior HCT outcomes.

#### *Implications for $\beta$ -cell failure and $\alpha$ -cell dysregulation during PTDM development*

Glucose homeostasis is maintained by the coordinated secretion of insulin by pancreatic  $\beta$ -cells and glucagon by  $\alpha$ -cells (27, 28). In addition to blood glucose, this process is regulated by the gut-derived incretin hormones glucagon-like peptide-1 (GLP-1) and glucose-dependent insulinotropic polypeptide (GIP) which are secreted postprandially, promoting insulin release and glucagon suppression (29). In a prospective observational cohort study funded by the NHLBI a standard OGTT was performed on HCT recipients without established diabetes before and 90 days after transplant (Figure 1). Although insulin levels appear similar before and after transplant in the 2 groups, only in patients maintaining post-transplant euglycemia are  $\beta$ -cells able to prevent significant glucose excursions during the challenge (bottom panel B). Compared to pre-transplant values, blood sugars were elevated at all time points after HCT with no corresponding increase in insulin secretion by the PTDM group (top panel A). These data are most consistent with the development of a new  $\beta$ -cell defect after HCT.

Glucagon is secreted in response to hypoglycemia where it promotes hepatic glycogen breakdown and gluconeogenesis. Our preliminary data suggests that PTDM patients have elevated fasting and post-prandial glucagon levels when compared to their pre-transplant values and when compared to individuals maintaining euglycemia after HCT. This inappropriate glucagon elevation in PTDM patients exists despite factors known to inhibit  $\alpha$ -cells including elevations in blood glucose, insulin, and GLP-1 (Figure 1). Taken together these data indicate a role for hyperglucagonemia and impaired  $\alpha$ -cell regulation in PTDM

[figure not shown]
**Figure 1. OGTT suggests  $\beta$ -cell failure and impaired glucagon suppression during PTDM after HCT. Representative data from 8 HCT recipients without a pre-transplant diagnosis of diabetes is shown. Blood glucose, insulin, C-peptide, glucagon, and GLP-1 were measured every 30 minutes for 2 hours during a standard OGTT performed before and 90 days after HCT. Median values are depicted and data is stratified for the development of new-onset PTDM (A) or maintenance of euglycemia (B).**

GLP-1 is an important regulator of glucagon suppression. As expected, after an oral glucose load, GLP-1 is secreted with a corresponding increase in insulin and decline in glucagon (Figure 1). We hypothesize that the exaggerated GLP-1 secretion in PTDM patients after transplant represents an incomplete compensatory mechanism meant to restore homeostasis which will be explored further in Aim 1B with possible therapeutic ramifications.

#### *PTDM is Th-1 skewed and characterized by altered ST2 signaling*

[figure not shown]
Elevated fasting C-peptide levels pre-transplant and PTDM development after HCT both predict inferior survival (1, 8). Our collaborators have demonstrated that pre-transplant elevations in the decoy receptor sST2 are seen with obesity and that high sST2 after HCT is a validated biomarker for non-relapse mortality due to immune dysregulation (30-32). Published literature indicates that low IL-33 levels are involved in insulin resistance in non-transplant animal models of diabetes (21, 22). Therefore we sought to examine sST2 as a predictor of PTDM independent of GVHD. In a group of HCT recipients without preexisting diabetes, serum sST2 was elevated at neutrophil engraftment in patients who were prospectively diagnosed with new-onset PTDM after HCT (Figure 2). This increase in engraftment sST2 was confirmed in a separate cohort of HCT recipients who were retrospectively diagnosed with PTDM (14). We also confirmed that the majority of PTDM diagnoses occurred before steroids exposure (67% in cohort 1 and 93% in cohort 2). Since PTDM generally occurs before steroids then steroids should not influence the development of PTDM for the majority. After adjustment for myeloablative chemotherapy and grade 3-4 acute GVHD (factors known to influence sST2 and survival), high engraftment sST2 ( $\geq 75^{\text{th}}$  percentile of combined cohorts 1 and 2) predicted increased PTDM (HR, 2.25; 95%CI, 1.07-4.75;  $P = 0.03$ ) and non-relapse mortality risk (HR, 8.54; 95%CI, 1.62-45.15;  $P = 0.01$ ) (14). Thus, the data suggests that dysregulation of the IL-33/ST2 axis may influence metabolic complications after HCT which in turn presages clinical GVHD, steroid exposure, and mortality.

**Figure 2. Increased sST2 after HCT is a validated PTDM predictor.**  
 Serum sST2 was measured by ELISA at engraftment in 36 euglycemic HCT recipients followed prospectively for PTDM (cohort 1). Results were confirmed in a second cohort of 26 patients without pre-existing diabetes retrospectively analyzed for PTDM (cohort 2).

[figure not shown]

Type 2 diabetes mellitus is characterized by systemic inflammation (15-18). Using established cytometric assays, we found that by day+10 after HCT inflammatory IFN- $\gamma$ + Th1 cells were increased in patients prospectively followed for PTDM (Figure 3). This inflammatory response in PTDM could be driven by IL-33/ST2 disequilibrium and upregulation of ST2 by Th1 cells following HCT (Figure 4). The net effect of this IL-33/ST2 signaling after HCT could be Th1 inflammation which overwhelms immune regulation and causes  $\beta$ -cell stress.

**Figure 3. PTDM is characterized by an inflammatory / Th-1 skewed environment.** A cohort of 18 HCT recipients were prospectively followed for PTDM. The frequency of circulating Th1 cells were determined by flow cytometry.

**Figure 4. ST2 is expressed by a significant population of Th1 cells but not Th17 cells.** HCT recipient PBMCs were stimulated for 5 hours with PMA/ionomycin/monensin. Cells were surface-stained, fixed and permeabilized and then intracellularly stained with an assay containing: CD14, CD3, CD4, ST2, IL-17, IFN- $\gamma$ , and amine viability dye. Viable CD3+CD4+ T cells were identified followed by gating on ST2 vs. IFN- $\gamma$  or IL-17 to determine the frequency of ST2+Th1 (A) or ST2+Th17 cells (B), respectively.

In summary, our data suggests that immune dysregulation and changes in IL-33/ST2 signaling contributes to the pathogenesis of PTDM which begins before transplant with compensatory  $\beta$ -cell changes followed by islet dysfunction manifesting as insulin insufficiency and hyperglucagonemia after HCT.

#### 4.0 Inclusion/Exclusion Criteria

##### *Inclusion Criteria for Patients:*

- Age  $\geq$  18 years
- Patients undergoing MRD allogeneic HCT

##### *Exclusion Criteria for Patients:*

- Patients who have not received an allogeneic HCT
- Recent or current history of diabetes mellitus, defined as: 1) diabetes therapy within 6 months of enrollment, or 2) fasting blood glucose at “pre-admit” (screening) visit  $\geq 126\text{mg/dL}$
- Pregnancy or breastfeeding
- Unrelated donor, umbilical cord blood, mismatched, or haploidentical transplants
- Patients receiving T cell depletion or thymoglobulin as part of their transplant
- Patients on established, chronic corticosteroid therapy ( $> 10\text{ mg /day of prednisone or prednisone equivalent}$ ) prior to transplant. Established, chronic corticosteroid therapy is defined as daily dosing of  $> 10\text{ mg / day of prednisone or prednisone equivalent}$  for at least 2 weeks prior to the start of conditioning/chemotherapy or plans to continue pre-transplant corticosteroids ( $> 10\text{ mg /day of prednisone or prednisone equivalent}$ ) indefinitely after transplantation.
- Inability to give informed consent
- Any condition which, in the opinion of the investigator, might interfere with study objective
- Any reason which, in the opinion of the investigator, adds additional risk to the patient

*Additional exclusion criteria (Aim 1 only):*

- Diagnosis of diabetes by standard oral glucose tolerance testing prior to transplant (2-hour plasma glucose value  $\geq 200\text{ mg/dL}$ ).

*Inclusion Criteria for Donors:*

- Age  $\geq 18$  years
- Donors undergoing stem cell collection for match related allogeneic stem cell transplant

*Exclusion Criteria for Donors:*

- Individuals not donating stem cells
- Pregnancy or breastfeeding
- Inability to give informed consent
- Any condition which, in the opinion of the investigator, might interfere with study objective

## 5.0 Enrollment

Potential study candidates will be recruited from the Hematology-Oncology Clinics at the Vanderbilt Ingram Cancer Center (VICC) by a member of the research team prior to their allogeneic stem cell transplant. Potential participants including patients and donors will be identified at the time of acceptance for transplant by their treating physicians. Patients and donors who may qualify for participation will be provided a copy of the IRB-approved Informed Consent document to read. Subjects who express interest will then meet with a member of our research team during their regularly scheduled clinic visit. Interested subjects will be screened for inclusion and exclusion criteria. Standard of care laboratories (*i.e.* pregnancy test if indicated and fasting blood glucose) will be reviewed.

Those subjects who sign consent and who fulfill all inclusion and exclusion criteria will then be enrolled in the study.

## **6.0 Study Procedures**

[figure not shown]
### *Sources of materials- Donors*

*Donors* who have given informed consent will undergo standard of care evaluations or study visits at either the Outpatient Transplant Unit or the inpatient Myelosuppression Unit at Vanderbilt University Medical Center. Study blood will be obtained once prior to beginning the stem cell mobilization procedure. A single blood draw of 50-60 ml will be collected once. Venous blood will be obtained via peripheral venipuncture and preferably will be collected during routine laboratory analysis. Samples will be coded with a unique alphanumeric identifier. Clinical information and research data will be obtained by donor interview, medical chart review, and from laboratory testing. Information will be stored in a password-protected electronic database. After the blood draw no further testing will be performed on the donor.

A single sample of 50-60 mL of blood will be collected from the donor at one time point during this study.

### *Sources of materials- Patients*

Study participants who have given informed consent will undergo standard of care evaluations or study visits at either the Outpatient Transplant Unit, the inpatient Myelosuppression Unit, or the Clinical Research Center (CRC) at Vanderbilt University Medical Center. Two oral glucose tolerance tests and 1 hyperglycemic clamp will be performed on separate days prior to transplant and then each procedure will be repeated once between day+80 to day+100 (+/- 10 days) after transplant (Figure 5). In addition to the 6 research visits, study blood will be obtained at the following timepoints: pre-transplant (prior to beginning chemotherapy), Day+10, Day+20, Day+30, and Day+90 (all +/- 7 days) (the day of stem cell infusion is considered Day 0). A total of 550 mL of blood will be collected from the patient over approximately 110 days (over 3 to 4 months). Blood will be drawn for research purposes at the same time as routine blood sampling when feasible. Venous blood will be obtained by accessing the central venous catheter using sterile technique or via peripheral venipuncture. Samples will be coded with a unique alphanumeric identifier at the time of collection so that patient identity will be available only to study investigators and research staff. Clinical information, outcomes, and research data will be obtained by patient interview, medical chart review, and from laboratory testing. Information will be stored in a password-protected electronic database.

**Figure 5. Study schema and timeline**

### OGTT

Two OGTTs (without and with GLP-1 infusion) will be performed prior to HCT and after an 8 hour overnight fast (water and medications allowed) in patients with a screening blood glucose < 126 mg/dL. Plasma samples will be analyzed for glucose, insulin, glucagon, C-peptide, GLP-1 every 30 minutes from Time -30 minutes to Time 120 minutes (6 time points) as per physician discretion. Remaining aliquots will be stored. At time 0, participants will ingest 75 g of water-free glucose dissolved in 300 mL of water. Pre-HCT patients will be categorized per the 2-hour OGTT plasma glucose value as normal (<140 mg/dL), impaired glucose tolerance (140-199mg/dL), or diabetic ( $\geq 200$  mg/dL) (33, 34). Study patients diagnosed with diabetes by standard OGTT prior to HCT will not be monitored for *de novo* PTDM. Study patients diagnosed with diabetes by standard OGTT prior to HCT will not undergo further testing as outlined in aim 1 after the diagnosis is made, however the immune / metabolic studies as outlined for aim 2 will be performed in these individuals.

The second OGTT procedure will be repeated on a different day with exogenous GLP-1 infusion using similar methods as described above. At Time -30 minutes, a 2.0 pmol/kg/min infusion of GLP-1 will be given IV and continued for the remainder of the procedure (150 minutes). This concentration of GLP-1 is well tolerated (35). GLP-1 (7-36) amide acetate will be purchased from Clinalfa, Bachem (Weil am Rhein, Germany). Vanderbilt Investigational Drug Service (IDS) has experience preparing this medication for use in clinical investigation (36). Biologically active GLP-1 is rapidly metabolized by the proteolytic enzyme DPP-4 with a half-life < 2 minutes in the circulation. Thus, the physiologic effects of GLP-1 should be negligible shortly after the infusion is stopped at time = 120 minutes (29).

A total of about 90 ml of blood will be drawn for the 2 OGTTs. The 2 OGTTs will be repeated after transplant between day +80 to day +100 +/- 10 days.

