### *Adipose tissue microdialysis*

During the OGTT without GLP-1 infusion, a microdialysis catheter will be inserted into abdominal subcutaneous adipose tissue using local anesthesia and sterile technique. At the start of the OGTT, the microdialysis pump containing T1 perfusion fluid (M Dialysis) will be infused at 1  $\mu$ l/min. After 60 minutes the microdialysate will be discarded and a fresh microdialysate sample will be obtained over 90 minutes. Samples will be collected on ice and stored at -80° C until analysis.

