### *Secondary analyses for Subaims 1A and 1B*

1) determining if glucagon secretion and OGTT results pre-transplant predict PTDM development (herein OGTT results refers to 2 hour blood glucose and peak/nadir/total hormone levels during OGTT), 2) determining if GLP-1 infusion increases insulin secretion and glucagon suppression compared to OGTT values without GLP-1, 3) comparing GSIS, glucagon suppression, and OGTT results at day +90 among patients with or without established PTDM, and 4) comparing the change in GSIS, glucagon suppression, and OGTT results at baseline to those determined at day +90 after transplant in the entire cohort or among groups stratified based on PTDM, conditioning regimen (ablative vs. reduced intensity) or for the presence or absence of acute GVHD treated with steroids.

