## Appendix A

### Study Table - Donor

	Baseline	Pre-Collection
Study Blood collection		X
Informed Consent	X	
Review of Eligibility	X	
Data Collection	X	X

Study Table - Patient

	Baseline	Pre-Transplant	Day 10 post-transplant	Day 20 post-transplant	Day 30 post-transplant	Day 80-100 post-transplant	D365 post-transplant	D730 post-transplant
Study Blood collection	X		X	X	X	X		
OGTT / Microdialysis - CRC visit		X				X		
OGTT / GLP-1 Infusion - CRC visit		X				X		
Hyperglycemic Clamp - CRC visit		X				X		
Informed Consent	X							
Review of Eligibility	X							
Data Collection	X	X	X	X	X	X	X	X

All dates for blood collection +/- 7 days, all dates for procedures / study visits +/- 10 days

Oral glucose tolerance testing and the hyperglycemic clamps will be performed on separate days as scheduling allows

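### The order of the standard and GLP-1 OGTTs is neither randomised nor balanced, so the secondary within-patient GLP-1 contrast can absorb order or time drift

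*Combined protocol and SAP*

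**What the plan says.** Section 6.0 (OGTT) plans two tests before transplant: "Two OGTTs (without and with GLP-1 infusion) will be performed prior to HCT". It then describes the GLP-1 test: "The second OGTT procedure will be repeated on a different day with exogenous GLP-1 infusion using similar methods". A patient found diabetic on the standard pre-transplant test "will not undergo further testing as outlined in aim 1 after the diagnosis is made". That gate makes sense only if the standard test comes first, although no sentence says so.

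For the post-transplant tests the same section says "The 2 OGTTs will be repeated after transplant between day +80 to day +100 +/- 10 days" and gives no order. The note under the study tables in Appendix A says "Oral glucose tolerance testing and the hyperglycemic clamps will be performed on separate days as scheduling allows". The Figure 5 schema is not shown in the text available.

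The two tests also differ in a second respect. Under Adipose tissue microdialysis: "During the OGTT without GLP-1 infusion, a microdialysis catheter will be inserted into abdominal subcutaneous adipose tissue". The hyperglycemic clamp section repeats the microdialysis after transplant.

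Section 10.2, secondary analyses for Subaims 1A and 1B, lists as item 2: "determining if GLP-1 infusion increases insulin secretion and glucagon suppression compared to OGTT values without GLP-1". The general statistical plan analyses matched data by paired t-test or signed rank test. It names no term for test order or position.

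**The concern.** A within-patient comparison of two test days isolates the GLP-1 effect only if nothing else differs systematically between those days. If GLP-1 is always given on the later day, the mean paired difference is the GLP-1 effect plus whatever changes on average between a first and a later OGTT: a repeat-test effect, changes in immunosuppression, or recovery. The data then cannot separate the two. The post-transplant window of day +80 to +100, plus or minus 10 days, runs from day +70 to day +110, so up to 40 days could separate the tests. No maximum gap is stated.

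A drift could therefore produce an apparent GLP-1 effect, hide a real one, or shift the estimate of its size. If the order is instead left to scheduling, it is uncontrolled and may depend on how well the patient is.

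**Working it through.** **Inputs from the plan (Section 10.1).** There are 34 evaluable patients, 17 per PTDM group. The SD of log glucagon AUC between patients is 0.73, alpha is 0.05 two-sided, and the Subaim 1B difference is 1.0 log unit (8.83 to 7.83).

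**Inputs assumed.** The documents give neither the within-patient correlation r nor the drift between tests. I take r from 0.3 to 0.8 and a drift of 5%, 10% or 20%, with log as natural log.

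**The plan's own figure.** The plan states no sample size for the GLP-1 contrast. Its Subaim 1B figure reproduces by the normal approximation: 2 × (1.96 + 0.84)² × (0.73/1.0)² = 8.4, so 9 per group. An exact t-test gives 77.9% power at 9 per group and 97.2% at the planned 17.

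**Drift in the labelled order.** The SD of the paired difference is SDd = 0.73 × √(2(1 − r)), and SE = SDd/√34. With no GLP-1 effect, the noncentrality is ln(1 + drift)/SE on 33 degrees of freedom. At r = 0.7, SDd = 0.565 and SE = 0.097, so a 10% drift gives 0.0953/0.097 = 0.98.

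| r | SE | 5% drift | 10% drift | 20% drift |
|---|---|---|---|---|
| 0.3 | 0.148 | 6.2% | 9.6% | 22.3% |
| 0.5 | 0.125 | 6.7% | 11.5% | 29.3% |
| 0.7 | 0.097 | 7.8% | 15.9% | 44.7% |
| 0.8 | 0.079 | 9.2% | 21.5% | 60.8% |

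Entries are the chance of a significant paired test; 5% is nominal.

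**Mixed order.** If scheduling put GLP-1 second in 75% and first in 25%, unrelated to patient state, the net drift is (0.75 − 0.25) = half. At r = 0.7 a 20% drift then gives 0.091/0.097 = 0.94 and about 15% false positives. A 10% drift gives about 8%.

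**Randomised order with a position term.** Degrees of freedom fall from 33 to 32. The detectable effect at 80% power moves from 0.4950 to 0.4955 SDd, and power from 80.0% to 79.9%. In a 20,000-run simulation with an order effect of 0.3 or 0.5 SDd, the fixed order gave 39.5% or 81.0% false positives. Random order gave 5.2% or 4.9% with no bias.

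**Catheter.** An assumed catheter effect of 0.3 SDd gave about 40% false positives under both designs.

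**Cost to the Subaim 1B primary, if it uses the standard OGTT.** With half the patients shifted by k SD, the SD becomes 0.73 × √(1 + k²/4). At k = 0.5 this is 0.7525, and power falls from 97.2% to 96.4%. If 10% or 20% complete only their first post-transplant OGTT, half of them lose the standard test. That leaves 17 × 0.95 = 16.15 or 17 × 0.90 = 15.3 per group, with power 96.5% or 95.5%.

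**Effect on item 4 (change from baseline to day +90).** The standard test would be first in everyone before transplant and second in half afterwards, so half the position effect enters the unadjusted mean change. Under the balanced crossover, the position effect has variance SDd²/34. Removing half of it adds ¼ × SDd²/34. If the change has the same SD as the paired difference, its SE rises by √1.25 = 1.12, or 12%.

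**The case against.** The strongest objection is that the text fixes no order after transplant. The word second in Section 6.0 may only name the second type of test, and Figure 5 is not shown. This stands. A reader might infer that GLP-1 is always given second, so that the drift figures describe what will happen. The documents do not support that: the figures apply only if the labelled order is followed, and they fall if the order is mixed. Nor do the documents show that any drift exists. Changes that average to zero across patients add noise, not bias.

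A second objection is that a null GLP-1 effect is of little interest, because Section 3.0 already treats GLP-1 as promoting insulin release and glucagon suppression. This stands in part. The bias in the estimated size is the same whatever the true effect is. The Subaim 1B hypothesis of incomplete suppression in PTDM points to a between-group comparison, where a common additive order or catheter effect cancels. A drift that differs between the groups would not cancel.

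A third objection is that standard-first has a purpose after transplant too. It protects the standard test, and the microdialysis done with it, in patients who manage only one visit, and it keeps that test in the same position before and after transplant. This also stands, and the fix must allow for it. The computed loss for Subaim 1B is under 2 points, but item 4 needs an adjustment.

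A reader might also infer that the primary outcomes are compromised. They are not within-patient GLP-1 contrasts, so that does not follow.

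**Conclusion.** The point holds for one secondary analysis. The readable plan does not randomise, balance or model the order of the two OGTTs. Before transplant, standard-first is implied; after transplant, the order is unspecified. If the labelled order is followed, item 2 estimates the GLP-1 effect plus any common drift. At correlations of 0.5 to 0.7, false-positive rates are 11.5% to 15.9% for a 10% drift and 29.3% to 44.7% for a 20% drift. These rest on assumed drift and correlation, on 34 complete pairs, and on the Section 10.1 SD, which comes from preliminary data in PTDM patients.

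The catheter is a separate confounder. It is tied to the test without GLP-1 every time, and randomising the order does not remove it. The change is a cheap improvement that should be made before further post-transplant tests, because analysis cannot recover an order effect if every patient is tested in the same order.

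**What to change.** 1. For the day +80 to +100 tests, assign the order of the two OGTTs 1:1 from a random list, stratified by PTDM status at that time. Record both test dates and set a maximum gap.
2. Analyse item 2 with a mixed model that includes test position. The half-life under 2 minutes cited in Section 6.0 and the use of separate days make drug carry-over negligible, so the crossover model is reasonable.
3. State which post-transplant OGTT supplies the Subaim 1B primary. If it is the standard test, adjust the glucagon AUC comparison for position. Adjust the item 4 change as well.
4. Before transplant, state the standard-first order that the gate implies, and report that GLP-1 contrast as confounded with order.
5. State as a limitation that the catheter is present only in the test without GLP-1.

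The cost is a short amendment, one list, one degree of freedom and less scheduling freedom, with no added patients or visits. Subaim 1B power falls from about 97% to 95.5–96.5% if 10–20% of patients complete only one post-transplant OGTT. The adjusted whole-cohort change in item 4 is somewhat less precise, with an SE about 12% larger under the assumption shown.
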